**Definition of SAE**

If an event is not an AE per definition above, then it cannot be an SAE even if serious conditions are met (eg, hospitalization for signs/symptoms of the disease under study, death due to progression of disease).

**A SAE is defined as any untoward medical occurrence that, at any dose:****a. Results in death****b. Is life-threatening**

The term 'life-threatening' in the definition of 'serious' refers to an event in which the participant was at risk of death at the time of the event. It does not refer to an event, which hypothetically might have caused death, if it were more severe.

**c. Requires inpatient hospitalization or prolongation of existing hospitalization**

In general, hospitalization signifies that the participant has been detained (usually involving at least an overnight stay) at the hospital or emergency ward for observation and/or treatment that would not have been appropriate in the physician's office or outpatient setting. Complications that occur during hospitalization are AE. If a complication prolongs hospitalization or fulfills any other serious criteria, the event is serious. When in doubt as to whether "hospitalization" occurred or was necessary, the AE should be considered serious.

Hospitalization for elective treatment of a pre-existing condition that did not worsen from baseline is not considered an AE.

**d. Results in persistent disability/incapacity**

The term disability means a substantial disruption of a person's ability to conduct normal life functions.

This definition is not intended to include experiences of relatively minor medical significance such as

uncomplicated headache, nausea, vomiting, diarrhea, influenza, and accidental trauma (eg, sprained ankle), which may interfere with or prevent everyday life functions but do not constitute a substantial disruption.

**e. Is a congenital anomaly/birth defect****f. Other situations:**

Medical or scientific judgment should be exercised in deciding whether SAE reporting is appropriate in other situations such as important medical events that may not be immediately life-threatening or result in death or hospitalization but may jeopardize the participant or may require medical or surgical intervention to prevent one of the other outcomes listed in the above definition. These events should usually be considered serious.

Examples of such events include invasive or malignant cancers, intensive treatment in an emergency room or at home for allergic bronchospasm, blood dyscrasias, or convulsions that do not result in hospitalization, or development of drug dependency or drug abuse.

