### Assessment of Intensity

Investigators assess or "grade" severity of each AE and SAE of their participants. The National Institutes of Health suggest a 5-scale rating to adequately capture the severity (NIH, 2017). The 5-scale rating consists of: mild, moderate, severe, life-threatening, death.

The 5 point grading scale of mild/moderate/severe/life-threatening/death will be used for all adverse events.

The investigator will assess intensity for each AE and SAE reported during the study and assign it to 1 of the following categories:

- Mild: An event that is easily tolerated by the participant, causing minimal discomfort, and not interfering with everyday activities.
- Moderate: An event that causes sufficient discomfort and interferes with normal everyday activities.
- Severe: An event that prevents normal everyday activities. An AE that is assessed as severe should not be confused with an SAE. Severe is a category utilized for rating the intensity of an event; and both AE and SAE can be assessed as severe.
- Life-threatening: An event that would indicate urgent intervention is required to prevent complete loss of vision or the eye
- Death

Adverse events are also coded using the Medical Dictionary for Regulatory Activities (MedDRA), which consists of highly specific standardized terminology that was developed by ICH to facilitate to adequately capture the important information needed to assess adverse events and help to assure participant safety and medical understanding of the event.

Citation: U.S. Department of Health and Human Services, National Institutes of Health, National Institute of Allergy and Infectious Diseases, Division of AIDS. Division of AIDS (DAIDS) Table for Grading the Severity of Adult and Pediatric Adverse Events, Corrected Version 2.1. [July 2017]. Available from:

<https://rsc.niaid.nih.gov/sites/default/files/daidsgradingcorrectedv21.pdf>

An event is defined as 'serious' when it meets at least 1 of the predefined outcomes as described in the definition of an SAE, NOT when it is rated as severe.

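### Protocol Appendix 4 defines life-threatening in two incompatible ways and does not say whether an event graded as threatening the eye is an SAE

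*Protocol*

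**What the plan says.** The SAP (Section 5) makes the frequency and severity of ocular and systemic AEs and SAEs the primary safety variable. It refers to Protocol Appendix 4 for the definitions.

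The SAE criteria there are death (a), life-threatening (b), hospitalization (c), persistent disability (d), congenital anomaly (e) and other situations (f).

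- Criterion b concerns "an event in which the participant was at risk of death at the time of the event".
- Criterion c turns on admission. Where it is doubtful whether admission occurred or was needed, "the AE should be considered serious".
- Criterion d has this gloss: "The term disability means a substantial disruption of a person's ability to conduct normal life functions".
- Criterion f opens "Medical or scientific judgment should be exercised in deciding whether SAE reporting is appropriate in other situations such as important medical events". It reaches events that "may require medical or surgical intervention to prevent one of the other outcomes listed in the above definition", and adds that these are normally to be treated as serious. Its illustrations begin "Examples of such events include invasive or malignant cancers, intensive treatment in an emergency room" and go on to bronchospasm, blood dyscrasias, convulsions and drug dependency or abuse.

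The section on assessment of intensity, in the same appendix, has five categories. The highest short of death is labelled life-threatening and described as "An event that would indicate urgent intervention is required to prevent complete loss of vision or the eye". The section closes by saying that an event is serious when it meets an SAE outcome, and not because it is rated severe.

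**The concern.** In a trial of intravitreal injections, the harms of most interest threaten the eye rather than life. The intensity scale recognises them. The SAE criteria name neither vision nor the eye, and they use the scale's own label for something else. An investigator who has just graded an event life-threatening must then decide whether SAE criterion b, which carries the same words, is met. The appendix gives no answer for that grade; its only statement on the link between intensity and seriousness concerns the severe category.

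Two things depend on the decision. One is the count of ocular SAEs, which is part of the primary safety variable. The other is the reporting route: Protocol Section 8.1 sets a time limit for reporting SAEs to the sponsor, and Section 8.3.1 places regulatory duties on the sponsor once an SAE is notified.

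**Working it through.** The plan gives no figure to reproduce, so the check is mainly a reading of the text.

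**Step 1: the two meanings.** Criterion b requires "an event in which the participant was at risk of death at the time of the event". The intensity category requires "An event that would indicate urgent intervention is required to prevent complete loss of vision or the eye". An event that endangers an eye but not life meets the second and fails the first. A systemic event that endangers life but not an eye meets the first, and the description of the intensity category does not fit it. Neither definition contains the other.

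**Step 2: the routes to SAE status.** Take an AE placed in that intensity category, with no risk of death.

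| Course of the event | Route in the visible Appendix 4 text |
|---|---|
| Participant admitted, or admission in doubt | c |
| No admission; severe visual loss becomes lasting | d can apply, once persistence is established |
| No admission; sight saved, or outcome not yet known | f only |
| Investigator equates the grade with criterion b because the label is the same | b ticked, although its definition is not met |

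The third row is the gap. It also covers the early phase of events that later move to the second row, which is when prompt reporting matters.

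**Step 3: how firm criterion f is.** Preventing lasting blindness in an eye can be read as preventing persistent disability, so the clause "may require medical or surgical intervention to prevent one of the other outcomes listed in the above definition" can take the event in. The reader has to supply two links: that threatened sight in one eye counts as threatened disability under criterion d, and that the general presumption of seriousness holds in the case at hand. No example under f is ocular.

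**Step 4: divergence.** Site A reads the label as criterion b and ticks SAE. Site B reads b as risk of death, sees no ocular example under f, and leaves the box empty. Site C applies f and ticks SAE. Each can point to text in the appendix, although site A relies on the label rather than on b's definition.

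**Step 5: scale of one classification.** Input: 15 participants per group, 30 in total (Protocol Section 2 and Synopsis).

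- Per group: 1/15 = 6.7 percentage points. Overall: 1/30 = 3.3 percentage points.
- Exact 95% interval for 0/15: upper limit 1 − 0.025^(1/15) = 21.8%.
- Exact 95% interval for 1/15: lower limit 1 − 0.975^(1/15) = 0.2%. The upper limit solves (1−p)^15 + 15p(1−p)^14 = 0.025, giving 31.9%.

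These figures show what one event does to the table. They do not show how likely misclassification is, and the documents give no event rate.

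**The case against.** The strongest reply is that criterion f already covers the case. It includes intervention to prevent a listed outcome, persistent disability is a listed outcome, such events are presumed serious, and the examples are not exhaustive. Much of this stands. A reader might infer that an eye-threatening event is an SAE only at the investigator's free discretion. The documents do not support that: criterion c applies on admission with doubt resolved as serious, criterion d can apply to lasting loss, and f starts from a presumption. What remains is that the presumption is not a rule and that its application to sight has to be inferred.

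A reader might also infer that the protocol has no ocular rule at all. That cannot be asserted. Section 8.5.2, which introduces guidance on reporting possible AEs affecting vision, is redacted, as is the SAE reporting block in Appendix 4. Either may contain such a rule. Hidden text would still not remove the double meaning visible in the appendix.

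A third inference is that ocular SAEs will be under-reported and signals lost. The shared label can just as well lead to over-reporting through criterion b. An event not ticked as an SAE would still be recorded as an AE with its intensity grade.

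Finally, a reader might infer bias from unmasked classification. Protocol Section 6.3 names only the reading center and the vision examiner as masked, and the Day 28 injection is given only in the low-dose group with no sham described. It is therefore likely that the investigator knows the group. That is an inference: the documents do not say so, and the point does not depend on it.

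**Conclusion.** The concern holds as a defect in the visible Appendix 4 text. One term has two incompatible meanings, and no visible rule maps the highest non-fatal intensity category to SAE status. Sole reliance on criterion f is limited to eye-threatening AEs managed without admission and without established lasting disability. For those, sites following the text can classify the same event differently in either direction.

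The effect is on the consistency of the ocular SAE count and on whether the SAE reporting clock starts, not on whether the event is recorded. One event is worth 6.7 percentage points in a group of 15. The conclusion assumes full enrollment of 15 per group for that figure, and that the redacted passages contain no mapping rule. If they do contain one, the remaining task is to reconcile the term and refer to the rule from Appendix 4.

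**What to change.** 1. Reconcile the term between criterion b and the intensity scale. For example, label the intensity category sight-threatening or life-threatening, and let its description cover both the present ocular wording and risk of death as in criterion b.
2. Add to criterion f that any AE assigned the intensity grade described as "An event that would indicate urgent intervention is required to prevent complete loss of vision or the eye" is reported as an SAE, as an important medical event. Keep the urgency and the completeness of the threatened loss in that wording. A looser phrase, such as any intervention to prevent visual loss, could take in vision decline treated under the rescue provisions wherever that counts as an AE.
3. Add ocular examples to criterion f and keep the systemic ones, since systemic SAEs belong to the same primary variable.
4. Add an edit check that raises a query when this grade is entered and the SAE box is not ticked.

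The cost is a few sentences in Appendix 4 and one edit check. The downside is possibly a few more SAE reports.

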## Recording AE and SAE

### AE and SAE Recording

- When an AE/SAE occurs, it is the responsibility of the investigator to review all documentation (eg, hospital progress notes, laboratory, and diagnostics reports) related to the event.
- The investigator will then record all relevant AE/SAE information in the CRF.
- It is **not** acceptable for the investigator to send photocopies of the participant's medical records to the medical monitor in lieu of completion of the Sponsor's AE/SAE CRF page.
- There may be instances when copies of medical records for certain cases are requested by the medical monitor. In this case, all participant identifiers, with the exception of the participant number, will be redacted on the copies of the medical records before submission to safety team.
- The investigator will attempt to establish a diagnosis of the event based on signs, symptoms, and/or other clinical information. In such cases, the diagnosis (not the individual signs/symptoms) will be documented as the AE/SAE.

### Assessment of Intensity

Investigators assess or "grade" severity of each AE and SAE of their participants. The National Institutes of Health suggest a 5-scale rating to adequately capture the severity (NIH, 2017). The 5-scale rating consists of: mild, moderate, severe, life-threatening, death.

The 5 point grading scale of mild/moderate/severe/life-threatening/death will be used for all adverse events.

The investigator will assess intensity for each AE and SAE reported during the study and assign it to 1 of the following categories:

- Mild: An event that is easily tolerated by the participant, causing minimal discomfort, and not interfering with everyday activities.
- Moderate: An event that causes sufficient discomfort and interferes with normal everyday activities.
- Severe: An event that prevents normal everyday activities. An AE that is assessed as severe should not be confused with an SAE. Severe is a category utilized for rating the intensity of an event; and both AE and SAE can be assessed as severe.
- Life-threatening: An event that would indicate urgent intervention is required to prevent complete loss of vision or the eye
- Death

Adverse events are also coded using the Medical Dictionary for Regulatory Activities (MedDRA), which consists of highly specific standardized terminology that was developed by ICH to facilitate to adequately capture the important information needed to assess adverse events and help to assure participant safety and medical understanding of the event.

Citation: U.S. Department of Health and Human Services, National Institutes of Health, National Institute of Allergy and Infectious Diseases, Division of AIDS. Division of AIDS (DAIDS) Table for Grading the Severity of Adult and Pediatric Adverse Events, Corrected Version 2.1. [July 2017]. Available from:

<https://rsc.niaid.nih.gov/sites/default/files/daidsgradingcorrectedv21.pdf>

An event is defined as 'serious' when it meets at least 1 of the predefined outcomes as described in the definition of an SAE, NOT when it is rated as severe.

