5 SAFETY ANALYSES

All safety analyses will be performed using the Safety Population.

The primary safety variable is the incidence and severity of ocular and systemic AEs and SAEs. MedDRA Version 26.1 (September 2023) nomenclature will be used to code adverse events. The number and percent of participants reporting ocular and systemic AEs/SAEs will be tabulated based on the MedDRA System Organ Class and Preferred Term. Summary tables will be generated for all AEs regardless of causality as well as for treatment-related AEs.

The following safety data will be analyzed and presented in tabular format:

- Overview of Treatment Emergent Adverse Events
- Summary of Adverse Events by System Organ Class and Preferred Term
- 

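### The Life-threatening intensity grade is defined only by threat to sight or the eye, although the scale applies to all adverse events

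*Protocol*

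**What the plan says.** Protocol Appendix 4, Assessment of Intensity, names five grades, which it presents as an outside suggestion: "The 5-scale rating consists of: mild, moderate, severe, life-threatening, death". It then adopts them without limiting the body system: "The 5 point grading scale of mild/moderate/severe/life-threatening/death will be used for all adverse events". The instruction to sites is "The investigator will assess intensity for each AE and SAE reported during the study and assign it to 1 of the following categories", followed by the protocol's own definitions.

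- Mild and Moderate are defined by how well the event is tolerated and how far it disturbs daily life.
- The third grade is "Severe: An event that prevents normal everyday activities".
- The fourth is "Life-threatening: An event that would indicate urgent intervention is required to prevent complete loss of vision or the eye".
- Death has no further definition.

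The same appendix uses the fourth grade's label a second time, as criterion b of the SAE definition: "The term 'life-threatening' in the definition of 'serious' refers to an event in which the participant was at risk of death". Assessment of Intensity keeps the two classifications apart: "An event is defined as 'serious' when it meets at least 1 of the predefined outcomes", and not when it is rated severe.

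On the analysis side, SAP Section 5 states: "The primary safety variable is the incidence and severity of ocular and systemic AEs and SAEs". SAP Section 5.1 refers to Protocol Appendix 4 for how AEs are recorded and evaluated. The readable SAP has no grading definition of its own.

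**The concern.** The scope of the scale and the definition of its fourth grade do not match. The scale is compulsory for all AEs, yet the highest non-fatal grade can be reached only through the eye. Systemic events are clearly in scope: the primary endpoint in Protocol Section 4 covers ocular, systemic and serious events, and Appendix 4's own examples of important medical events include bronchospasm, blood dyscrasias and convulsions.

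What is at stake is the severity half of the primary safety variable. Systemic events that endangered life would be reported one grade too low or lower, and ocular events that did not endanger life would carry a label suggesting that they did. Some investigators may follow the written definition and others the ordinary meaning of the label. Like events could then be graded differently across the sites of a multi-center trial.

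**Working it through.** The plan states no figure on this point, so the main check is to apply the written definitions to test cases.

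**Case A: a systemic event with risk of death, survived, with no threat to the eye.**
- Death: not met, because the participant survived.
- Life-threatening: not met, because the only criterion is the need for urgent action to save sight or the eye.
- Severe: met if the event stops everyday activities.
- Moderate or Mild: possible if it does not. An abnormal laboratory finding can be an AE under Appendix 4, and a dangerous one need not disturb daily life.

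Severe is therefore the ceiling, and the literal grade may be lower.

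**Case B: an ocular event threatening complete loss of vision, with no risk of death.**
- The intensity grade is Life-threatening.
- SAE criterion b is not met, because it requires risk of death. The event may still be serious under another criterion, such as persistent disability or an important medical event.

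**Does another readable passage supply a systemic criterion for the fourth grade?**
- SAE criterion b: no. It restricts its meaning to the definition of serious, and the intensity section separates the two.
- The external grading table cited in the intensity section: its contents are not in the documents. The section writes out its own categories and tells investigators to use those.
- The SAP: no. Section 5.1 points back to Appendix 4.

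**Size from the documents alone.** Grades with no criterion that a systemic event can meet: 1 of 5, or 1 of the 4 non-fatal grades.

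**Size in a severity table, if there is one.** The inputs are 15 participants per group (Protocol Section 2, Schedule of Activities) and at most 30 overall (Protocol Section 1). If each participant is counted once at the worst grade, one misgraded participant moves the Severe row and the fourth-grade row, in opposite directions, by
- 1/15 = 6.7 percentage points within the group;
- 1/30 = 3.3 percentage points overall.

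**Expected number.** The documents give no rate for Case A. For N participants and a rate p, with every investigator grading literally, the expected number misgraded is N × p. With N = 30 this stays below one for any p below 1/30 = 3.3%. For an assumed p of 0.5% to 2%, it is 30 × 0.005 = 0.15 to 30 × 0.02 = 0.6. If only some investigators grade literally, it is smaller. These rates are assumptions, and the fault in the text does not depend on them.

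**The case against.** The strongest case on the other side is that little of practical weight depends on the label. A survived event with risk of death is still an SAE under criterion b. SAP Section 5 tabulates events by System Organ Class and Preferred Term, and SAP Section 2.6 presents data mainly as listings. With at most 30 participants, a reader would see the event as a systemic SAE whatever its grade. The protocol's primary endpoint concerns the occurrence of events, and only SAP Section 5 adds severity. All of this stands, and it is why the point is minor. It does not make the grade right: coding shows which organ was involved, not how intense the event was.

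It is also fair that no severity-by-group table can be seen. The list of tables in SAP Section 5 ends in an empty bullet, and Protocol Section 9 is not readable. The 6.7-point figure is therefore conditional on such a table. Nor can anyone tell from the documents whether CRF instructions or the cited external table gave sites a systemic criterion in practice. The finding concerns the definitions as listed.

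Three stronger readings are tempting, and the documents do not support them.

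- A reader might infer that life-threatening systemic events could escape SAE reporting. They could not: seriousness is judged on its own criteria, separately from intensity.
- A reader might infer that Appendix 4 holds two conflicting rules for one classification. It does not. One term has two meanings in two separate classifications, and the defect lies within the intensity scale, between its scope and its fourth definition.
- A reader might infer a substantial chance that the results will be distorted. Any such probability would rest on a rate and a share of literal grading that the documents do not give.

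**Conclusion.** The concern holds as a minor inconsistency. As written, the fourth intensity grade does not fit a scale that is required for all adverse events: survived systemic events with risk of death are capped at Severe, and sight-threatening events without risk to life are called Life-threatening. One of five grades is affected. The consequence is confined to reported intensity, which SAP Section 5 makes part of the primary safety variable. AE incidence and SAE classification are untouched.

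The textual conclusion rests only on the readable definitions in Appendix 4. The shift of 6.7 points per group assumes 15 participants per group and a table that counts each participant once by severity. The view that fewer than one participant is likely to be affected assumes a rate of such events below about 3.3%.

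**What to change.** Broaden the fourth grade and keep the scale at five grades. It should cover both (a) events in which the participant was at risk of death and (b) ocular events needing urgent intervention to avert complete loss of sight or of the eye. A label such as *Life-threatening or sight-threatening* would describe both. Use that label wherever the intensity section names the grades, and on the CRF. Where the section reports the outside suggestion, mark the label as the study's adaptation. The other four grades can stay as they are.

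Under (a), a systemic event in the fourth grade will also meet SAE criterion b. That is acceptable, but the text should keep saying that seriousness is decided on its own criteria.

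In the SAP, state that intensity is shown separately for ocular and systemic AEs wherever it is listed or tabulated. Section 5 already refers to both kinds of event, so this is a short addition.

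If events have already been graded, re-check two sets: every SAE meeting criterion b, whatever its current grade, and every AE graded Severe or Life-threatening. The first set is needed because a risk-of-death event may have been graded below Severe.

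The cost is a small amendment to Appendix 4 with any IRB/IEC review it needs, a CRF label update, a notice to sites, one sentence in the SAP and the limited re-check.
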